9.1.2 Serious adverse events

An SAE is defined as any adverse event [appearance of (or worsening of any pre-existing)] undesirable sign(s), symptom(s) or medical conditions(s) which meets any one of the following criteria:

- fatal
- life-threatening

Life-threatening in the context of a SAE refers to a reaction in which the subject was at risk of death at the time of the reaction; it does not refer to a reaction that hypothetically might have caused death if it were more severe (please refer to the ICH-E2D Guidelines).

- results in persistent or significant disability/incapacity
- constitutes a congenital anomaly/birth defect
- requires inpatient hospitalization or prolongation of existing hospitalization, unless hospitalization is for:
 - routine treatment or monitoring of the studied indication, not associated with any deterioration in condition (coronary heart disease, cerebrovascular disease or peripheral vascular disease).
 - elective or pre-planned treatment for a pre-existing condition that is unrelated to the indication under study and has not worsened since signing the informed consent
 - social reasons and respite care in the absence of any deterioration in the subject's general condition
 - treatment on an emergency outpatient basis for an event not fulfilling any of the definitions of a SAE given above and not resulting in hospital admission
- is medically significant, e.g. defined as an event that jeopardizes the subject or may require medical or surgical intervention to prevent one of the outcomes listed above

Medical and scientific judgment should be exercised in deciding whether other situations should be considered serious reactions, such as important medical events that might not be immediately life threatening or result in death or hospitalization but might jeopardize the subject or might require intervention to prevent one of the other outcomes listed above. Such events should be considered as "medically significant". Examples of such events are intensive treatment in an emergency room or at home for allergic bronchospasm, blood dyscrasias or convulsions that do not result in hospitalization or development of dependency or abuse.

All malignant neoplasms will be assessed as serious under "medically significant" if other seriousness criteria are not met.

Any suspected transmission via a medicinal product of an infectious agent is also considered a serious adverse reaction.

All reports of intentional misuse and abuse of the product are also considered serious adverse event irrespective if a clinical event has occurred.

9.1.3 SAE reporting

To ensure subject safety, every SAE, regardless of causality, occurring after the subject has provided informed consent and until the last study visit must be reported to Sponsor/Investigator **within 24 hours** of learning of its occurrence.

The investigator/sponsor will report all serious, unexpected adverse events as an IND safety report to the FDA no later than 15 calendar days after the investigator/sponsor's initial receipt of this information. **Fatal or life-threatening unexpected experiences for which there is a possibility that the experience may have been caused by the drug will be reported by the investigator/sponsor to the FDA by telephone or facsimile transmission no later than 7 calendar days after receipt of this information.** An annual report which includes summaries of all IND safety reports will be submitted to the FDA each year in the annual report and to

Kiniksa Pharmaceuticals (IMP/Drug Manufacturer) by the investigator/sponsor. Investigator is responsible for evaluating all safety information available, and notify FDA and all investigators in an IND safety report of potentially serious risks from this clinical trial or any other source as soon as possible but no later than 15 calendar days after the sponsor/investigator receives the safety information and determines that the information qualifies for reporting.

If the SAE is not previously documented in the Investigator's Brochure or Package Insert (new occurrence) and is thought to be related to the study treatment, a CMO & PS Department associate may urgently require further information from the investigator for health authority reporting. Kiniksa may need to issue an Investigator Notification (IN) to inform all investigators involved in any study with the same study treatment that this SAE has been reported.

Suspected and Unexpected Serious Adverse Reactions (SUSARs) will be collected and reported to FDA.

Any SAEs experienced after the Completion Study should only be reported to sponsor/investigator

9.1.4 Pregnancy reporting

Pregnancies

To ensure subject safety, each pregnancy occurring after signing the informed consent must be reported to sponsor/investigator within 24 hours of learning of its occurrence. The pregnancy should be followed up to determine outcome, including spontaneous or voluntary termination, details of the birth, and the presence or absence of any birth defects, congenital abnormalities, or maternal and/or newborn complications. Newborn will be followed up just until birth according to guidelines as there was nothing observed in any studies that would suggest a fetal development risk.

Any SAE experienced during pregnancy must be reported.

9.1.5 Reporting of study treatment errors

Medication errors are unintentional errors in the prescribing, dispensing, administration or monitoring of a medicine while under the control of a healthcare professional, subject or consumer.

Study treatment errors and uses outside of what is foreseen in the protocol will be collected in the eCRF irrespective of whether or not associated with an AE/SAE and reported to Safety only if associated with an SAE.

9.1.6 Data Monitoring Committee

This study will include a data monitoring committee (DMC) which will function independently of all other individuals associated with the conduct of this clinical trial, including the site investigators participating in the study. The DMC will assess at defined intervals the progress

of a clinical trial, safety data, and critical efficacy variables and recommend to the sponsor/investigator whether to continue, modify or terminate a trial.

Summary reports will be provided to a DMC after the first 5 subjects have been reviewed, after 15 subjects have been reviewed, and after every 10 subsequent patients.

Specific details regarding composition, responsibilities, data monitoring and meeting frequency, and documentation of DMC reports, minutes, and recommendations will be described in a separate charter that is established between the sponsor/investigator and the DMC.

Schedule of Safety Assessments:

Data Collection and Database management

Activity	Study Day													60	Unscheduled
	-3 to 0	0	1	2	3	4	5	6	7	14	21	28			
Vital signs	X	X	X		X		X		X	X	X	X		X	
Medications	X	X	X						X	X	X	X		X	
Respiratory parameters	X	X	X						X	X	X	X		X	
Hypersensitivity reaction			X	X	X	X	X	X	X						
Anaphylaxis reaction (defined according to Sampson's criteria, Sampson HA et al., J Allergy Clin Immunol. 2006 Feb;117(2):391-7		X	X	X											
Secondary Infections	X	X	X						X	X	X	X	X	X	
Hematology (CBC + diff: assessment for leukopenia, neutropenia, and thrombocytopenia)	X				X				X			X		X	
Coagulation (PT, PTT, INR)	X														
Chemistry (lytes, BUN, glucose, CR)	X				X				X			X		X	
Liver profile (AST, ALT, Alb, AlkP, Tbili, Dbili: assessment for drug-induced liver injury according to Hy's law)	X				X				X			X		X	
Adverse events	X	X	X	X	X	X	X	X	X	X	X	X	X	X	

9.2 Data collection

De-identified data from this study will be shared within an Academic Consortium to enhance the ability to monitor safety and efficacy signals.

Mavri Covid 19 Protocol_3.0_ 25June2020

Data management will be coordinated by C5Research at the Cleveland Clinic. Data will be entered into a secure dedicated REDcap cloud database, and data analysis will be performed by C5Research.

Designated investigator staff will enter the data required by the protocol into the Electronic Case Report Forms (eCRF). The eCRFs have been built using fully validated secure web-enabled software that conforms to 21 CFR Part 11 requirements. Investigator site staff will not be given access to the EDC system until they have been trained. Automatic validation programs check for data discrepancies in the eCRFs, allow modification and/or verification of the entered data by the investigator staff.

The investigator/designee is responsible for assuring that the data (recorded on CRFs and entered into eCRF) is complete, accurate, and that entry and updates are performed in a timely manner. The Investigator must certify that the data entered are complete and accurate.

After final database lock, the investigator will receive copies of the subject data for archiving at the investigational site.

All data should be recorded, handled and stored in a way that allows its accurate reporting, interpretation and verification.

9.3 Site monitoring

The investigator must maintain source documents for each subject in the study, consisting of case and visit notes (hospital or clinic medical records) containing demographic and medical information, laboratory data, electrocardiograms, and the results of any other tests or assessments. All information on CRFs must be traceable to these source documents in the subject's file. The investigator must also keep the original informed consent form signed by the subject (a signed copy is given to the subject).

The investigator must give the monitor access to all relevant source documents to confirm their consistency with the data capture and/or data entry. Additional checks of the consistency of the source data with the CRFs are performed according to the study-specific monitoring plan. No information in source documents about the identity of the subjects will be disclosed.

10 Data analysis and statistical methods

10.1 Analysis sets

All patients who provide informed consent and are randomized will be included in the analysis. Specifically, patients who are randomized and do not receive study medication/placebo and patients who have the study infusion discontinued before completion will remain in the intention-to-treat analysis. However, we may also perform a secondary, exploratory modified intention to treat analysis that would include all patients that actually receive study drug or placebo. As noted above, for patients who are lost to follow-up, due diligence will be performed, and given the importance of reliable estimates of the treatment effect for planning futures, every effort will be made to document respiratory status and survival as outlined in the primary and secondary endpoints.

10.2 Subject demographics and other baseline characteristics

The number and percentage of patients who completed the study, who discontinued the study and the reason for discontinuation will be presented for all patients. The frequency (%) of patients with major protocol deviations as well as the criteria leading to data exclusion from analysis will be presented in separate tables, if applicable. Finally, the number of enrolled patients by site will be presented descriptively.

Baseline value is defined as the last non-missing assessment prior to the first dose of study drug unless specified otherwise.

Demographic and background characteristic variables will be summarized using descriptive summary statistics. Continuous variables will be summarized using n, mean, standard deviation, median, Q1 (25th percentile), Q3 (75th percentile), minimum, and maximum. Categorical variables will be summarized using frequency and percentage.

10.3 Analysis of the primary and secondary endpoints

Based on preliminary case-control data of patients with severe COVID-19 pneumonia treated with mavrilimumab, we estimate that 40% of patients in the placebo group will meet the primary endpoint compared to 80% of treated patients. A sample size of 30 patients per arm (60 total) will provide at least 80% power to detect this difference using a 2-sided alpha of 0.05.

The results of our study will inform treatment effect to aid in the planning of larger studies. The primary efficacy analysis will be on an intention-to-treat basis and include all patients who are randomized. Use of supplemental oxygen and vital status will be assessed daily up to day 14. Patients will be considered to have met the primary endpoint if the patient is alive at day 14 and has not used supplemental oxygen for at least 24 hours, regardless of whether or not the patient is still in the hospital (i.e. success=1). All other patients will be counted as not meeting the primary endpoint (i.e. success=0), including deaths on or before day 14 and patients for whom information cannot be ascertained (eg.lost to follow-up, withdrew consent, or otherwise missing information on the primary endpoint at day 14). This is analogous to imputing the worst case scenario for missing data.

The primary analysis will report the number and percentage of patients meeting the primary endpoint. The chi-square statistic will be used to test the difference between the two treatment groups. The time to freedom from supplemental oxygen will also be displayed geographically with a Kaplan Meier curve. A two-sided p value of < 0.049 will be considered statistically significant for the primary endpoint, though as noted, an important aspect of this study is to better define the magnitude of the treatment effect of our clinical outcomes to appropriately power larger studies.

The secondary endpoints are the proportion of patients alive at day 28 (i.e. success=1), and the proportion of patients alive and without respiratory failure at day 28 (i.e. success=1). Similar to the primary analysis, patients not meeting the this criteria in each of the secondary endpoints will be considered a failure (i.e. success=0), including deaths on or before day 28 and patients

for whom information cannot be ascertained (e.g. lost to follow-up, withdrew consent, or otherwise missing information on the secondary endpoint at day 28). This is analogous to imputing the worst case scenario for missing data.

The probability of patients achieving the secondary endpoint successfully will also be estimated using Kaplan-Meier estimates and displayed with survival curves. In addition, we do not plan to adjust for multiple hypothesis testing in our secondary and exploratory endpoints. Therefore, these results will be displayed as point estimates with 95% confidence intervals. These intervals should not be regarded as definitive for treatment effects. Finally, we plan to analyze the comparison between mavrilimumab 6 mg/kg versus placebo after all patients have reached day 14 (or have died or been discharged prior to day 14) to expeditiously inform whether a larger study should be undertaken.

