1.2 Purpose

The purpose of this prospective, proof-of-concept Phase 2, multicenter, blinded, randomized placebo controlled study is to demonstrate that early treatment with mavrilimumab prevents progression of respiratory failure in patients with severe COVID-19 pneumonia and clinical and biological features of hyper-inflammation. These results will lead to and inform a Phase III randomized placebo-controlled trial.

2 Objectives and endpoints

Primary Objective

To demonstrate that early treatment with mavrilimumab prevents progression of respiratory failure in patients with severe COVID-19 pneumonia and clinical and biological features of hyper-inflammation.

Secondary Objectives

- To evaluate mortality
- To evaluate the duration of hospitalization
- To evaluate safety of mavrilimumab

Primary Endpoint

The primary endpoint is the proportion of subjects alive and off of oxygen at day 14.

When hospitalized patients are off of oxygen, this will be documented as an oxygen saturation >90% for at least 5 minutes at rest. For patients that are discharged before day 14, a telehealth visit will be performed at day 14. For patients discharged **off** of oxygen before day 14, the day 14 visit will assess that they are off of oxygen. For patients who are discharged **on** oxygen before day 14, the decision to discontinue oxygen will be based on standard clinical care according to the health provider who prescribed oxygen therapy. The day 14 telehealth visit will assess whether the patient remains on oxygen, and “off of oxygen” will be defined as no supplemental oxygen use for at least the previous 24 hours.

Secondary Endpoints

The secondary end-points are alive at day 28, and the proportion of subjects alive and without respiratory failure at 28 days. Respiratory failure is defined as needing mechanical ventilation, non-invasive ventilation, or high-flow oxygen.

Exploratory Endpoints

- Mortality at day 14
- Mortality at day 60
- Proportion of patients in each category according to the following ordinal scale at day 7, 14, 21, and 28:
 1. Not hospitalized
 2. Hospitalized, no supplemental oxygen
 3. Hospitalized, on supplemental oxygen
 4. Hospitalized, requiring nasal high-flow oxygen or non-invasive ventilation
 5. Hospitalized, requiring ECMO, invasive mechanical ventilation or both
 6. Death
- Freedom from mechanical ventilation
- Duration of hospitalization
- Change in SOFA score at day 7, day 14, day 21, and day 28, or until discharge

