7.1 Visit schedule and assessments

The assessment schedule lists all of the assessments and indicates with an “X”, the visits when they are performed. All data obtained from these assessments must be supported in the subject’s source documentation.

Subjects should be seen for all visits/assessments as outlined in the assessment schedule or as close to the designated day/time as possible. Missed or rescheduled visits should not lead to automatic discontinuation. Subjects who prematurely discontinue the study for any reason should be scheduled for a visit as soon as possible, at which time all of the assessments listed for the final visit will be performed.

Clinically significant abnormalities must be recorded on the relevant section of the CRFs capturing medical history/current medical conditions/AE as appropriate.

Table 7-1 Assessment Schedule^{tt}

Activity	Study Day ^a													Unscheduled ^d
	-3 to 0 ^b	0	1	2	3	4	5	6	7	14	21	28 ^c	60	
Informed consent	X													
Demographics	X													
Reason for hospitalization (COVID-19 pneumonia)	X													
Medical history	X													
Eligibility	X													
Physical exam	X													X
Vital signs	X	X	X	X	X	X	X	X	X	X	X	X	X	
Body Temperature (Celsius)	X	X	X	X	X	X	X	X	X	X	X	X	X	
Body weight	X													
Height	X													
Electrocardiogram	X													X
Chest imaging (CXR or chest CT)	X													X
Clinical assessment (6 category ordinal scale) ^a	X	X	X	X	X	X	X	X	X	X	X	X	X	
SOFA score	X								X	X	X	X	X	
2019-nCoV test*	X								X	X	X	X	X	
Respiratory Virus Panel	X													
CRP	X	X	X	X	X	X	X	X	X	X	X	X	X	
LDH ^e	X	X	X	X	X	X	X	X	X	X	X	X	X	
D-Dimer ^e	X	X	X	X	X	X	X	X	X	X	X	X	X	
Ferritin ^e	X	X	X	X	X	X	X	X	X	X	X	X	X	
Troponin	X													
NT-proBNP	X													
Mechanical ventilation assessment	X	X	X		X		X		X	X	X	X	X	
Respiratory parameters ^g	X	X	X		X		X		X	X	X	X	X	

Activity	Study Day ^a													
	-3 to 0 ^b	0	1	2	3	4	5	6	7	14	21	28 ^c	60	Unscheduled ^d
TB screening ^h	X													
Pregnancy test ⁱ	X													
Hematology (CBC + diff)	X				X					X				X
Coagulation (PT, PTT, INR)	X													
Chemistry (lytes, BUN, glucose, CR)	X				X					X				X
Liver profile (AST, ALT, Alb, AlkP, Tbili, Dbili)	X			X					X					X
Urinalysis	X													X
Adverse events	X	X	X	X	X	X	X	X	X	X	X	X		X
Concomitant medications ^l	X	X	X	X	X	X	X	X	X	X	X	X		X
Assessment for “off of oxygen” as defined for the primary endpoint ^o														

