^g Includes FiO₂, SpO₂, Respiratory rate, note if ventilated or not, if yes collect PEEP; rescue therapy used (e.g., Flolan, proning, NM blockade, ECMO). For FiO₂, SpO₂, and PEEP, best and worst of daily value. Calculate P to F ratio best and worst for each day.

^h Done at Investigator's discretion; not expected to be used for decision to treat; not a mandatory test.

ⁱ Females of child-bearing potential only, urine or serum at investigator's discretion.

^j Includes complete blood count (CBC) and differential at screening and CBC on subsequent indicated days.

^l Prohibited medications include any cell-depleting biological therapies (e.g., anti-CD20) within 12 months prior to Day 0; or previous treatment with noncell-depleting biological therapies (such as anti-tumor necrosis factor [TNF], anakinra, anti-Interleukin [IL]-6 receptor [e.g. tocilizumab], or abatacept) within 8 weeks (or 5 half-lives, whichever is longer) prior to Screening, treatment with alkylating agents within 12 weeks prior to Screening, intramuscular, receipt of live (attenuated) vaccine within the 4 weeks before Day 0, treatment with cyclosporine A, azathioprine, cyclophosphamide, or mycophenolate mofetil (MMF) within 4 weeks of Screening. **Concomitant medications to track include: antipyretics, antibiotics related to secondary infections, and all investigational off-label therapies for COVID-19 for each subject (e.g. chloroquine, hydroxychloroquine, anti-IL-6, corticosteroids, remdesivir, lopinavir/ritonavir) along with time, dose, and duration of their administration.** Other concomitant medications will be recorded at baseline and daily thereafter while hospitalized until Day 7, at Day 14, Day 21 and Day 28. This information will be included in the final study report.

^o Assessed daily thru Day 14 if hospitalized. If the patient is discharged, assess at Day 14.

^m Document whether death occurred after withdrawal of care, and if so, reason for withdrawal of care.

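### Do Sections 2 and 10.3 leave it open how an inpatient is scored as off oxygen at Day 14?

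*Combined protocol and SAP*

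**What the plan says.** Section 2 states the endpoint: "The primary endpoint is the proportion of subjects alive and off of oxygen at day 14". It then describes how that status is established. For inpatients: "When hospitalized patients are off of oxygen, this will be documented as an oxygen saturation >90% for at least 5 minutes at rest". For the Day 14 telehealth visit of discharged patients, being off oxygen "will be defined as no supplemental oxygen use for at least the previous 24 hours".

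Section 10.3 gives the scoring. Success requires being alive at Day 14, and that the patient "has not used supplemental oxygen for at least 24 hours, regardless of whether or not the patient is still in the hospital". The next sentence closes the rule: "All other patients will be counted as not meeting the primary endpoint (i.e. success=0"). The failures include deaths and patients whose status cannot be ascertained, among them those with "otherwise missing information on the primary endpoint at day 14".

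In Table 7-1 (Section 7.1) the off-oxygen row points back to the status "as defined for the primary endpoint". Its footnote o gives timing only: "Assessed daily thru Day 14 if hospitalized. If the patient is discharged, assess at Day 14". A separate footnote to the same table, written expressly for the primary endpoint and for time to freedom from oxygen, calls for the ordinal scale and the presence of supplemental oxygen to be recorded each day in hospital through Day 14. It mentions no saturation test.

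**The concern.** Read side by side, the section that defines the endpoint gives inpatients a saturation check and no 24-hour window. The section that scores it gives them a 24-hour window and no saturation check. The schedule row sends site staff back to a definition without restating it.

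Two kinds of inpatient could then be classified differently: one weaned less than 24 hours before the Day 14 assessment who passes the check, and one free of oxygen for 24 hours whose saturation is 90% or lower. A third question is whether an absent or failed check counts as missing endpoint information, which Section 10.3 scores as failure.

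A site that completes the row from Section 2 and a central analyst who scores from Section 10.3 might disagree on the same patient. With 30 patients per arm, one patient can decide a result near the 0.049 threshold.

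**Working it through.** **1. Does Section 10.3 classify every inpatient?** Apply it to the disputed cases.

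| Inpatient at Day 14 | Section 10.3 result | Why |
|---|---|---|
| Weaned under 24 hours ago, passes the check | Failure | Has not completed 24 oxygen-free hours |
| 24 hours off oxygen, saturation 90% or lower | Success | No saturation condition in the rule |
| 24 hours off oxygen, check failed or not recorded | Success | Oxygen use and vital status are both known |

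No case is left without an answer. The third row is doubtful only if saturation is first assumed to be part of the endpoint. A failed check is also a recorded result, not missing data.

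**2. Does Section 2 compete with it?** The inpatient sentence takes patients who are already off oxygen and says how this is documented. The telehealth sentence says how off oxygen is defined, and its 24-hour definition matches Section 10.3.

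**3. Are the data for Section 10.3 collected?** Yes. The Table 7-1 footnote and Section 10.3 both call for oxygen use to be assessed daily to Day 14. The analyst can apply the 24-hour rule whatever the bedside check shows. The same daily record serves the time-to-freedom curve.

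**4. The plan's power figure.** Inputs from Section 10.3: 40% vs 80%, 30 per arm, two-sided 0.05, at least 80% power. With pooled rate 0.6, the normal approximation is

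power = Φ{[0.40 − 1.960·√(2·0.6·0.4/30)] / √[(0.4·0.6 + 0.8·0.2)/30]} = Φ{(0.400 − 0.248)/0.1155} = Φ(1.317) = 90.6%.

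At 0.049 it is 90.4%. Exact enumeration of the uncorrected chi-square test gives 90.5%, and with continuity correction 85.1%. The stated figure holds.

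**5. How much would the other reading matter?** The documents give no weaning times, so this is illustration only. Assume a constant weaning rate with no deaths, and let a fraction f of patients weaned in the last 24 hours still be inpatients. Take 40/80 as the success rates under the 5-minute check:

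- h = −ln(1 − r)/14, which is 0.0365 per day for r = 0.40 and 0.1150 for r = 0.80.
- Share scored differently: s = f·(e^(−13h) − e^(−14h)). At f = 1 this is 0.0223 on placebo and 0.0244 on mavrilimumab, or 0.67 and 0.73 patients of 30.
- Chance of at least one such patient among 60: 1 − (1 − s_placebo)^30·(1 − s_mavrilimumab)^30.

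| f | At least one of 60 differs | Opposite verdicts at 0.049 | Exact power, 5-minute vs 24-hour |
|---|---|---|---|
| 0.25 | 30% | 1.5% | 90.5% vs 90.3% |
| 0.50 | 51% | 2.6% | 90.5% vs 90.1% |
| 1.00 | 76% | 4.3% | 90.5% vs 89.7% |

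Verdicts and power come from exact enumeration of the three possible outcomes per patient (success under both rules, under the 5-minute rule only, under neither). If 40/80 is attached to the 24-hour rule instead (13 in place of 14 in h), opposite verdicts are 1.5%, 2.6% and 4.1%.

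**6. The planned result.** At 12 vs 24 of 30, chi-square = 0.16/0.016 = 10 and p = 0.0016. Losing one treated success (12 vs 23) gives p = 0.0040. Only nearer the threshold does one patient decide: 12 vs 20 gives p = 0.038, and 12 vs 19 gives p = 0.071.

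**The case for a change.** The strongest case for a change is that the saturation check stands under the primary-endpoint heading, no sentence says it is not scored, and a wording change would cost little. Section 10.3 also does not state when its 24 hours end. Step 5 covers only late weaning. If the check were an added condition and removed 5%, 10% or 20% of successes in each arm (assumed shares), power at 0.049 would fall to 86.2%, 81.3% or 70.6%.

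What stands is the difference in wording: Section 2 could have said that the check is a record only. The rest carries less weight. The power losses require a saturation condition that Section 10.3 does not contain. The 24 hours naturally end at the Day 14 assessment, as the telehealth wording in Section 2 confirms. Site and analyst are unlikely to pull apart, because data analysis is done at one centre (Sections 3 and 9.2) from daily oxygen data. Any remaining variation between sites should not favour an arm: assessors are blinded (Section 6.3) and randomization is stratified by site (Section 6.2.4).

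**Conclusion.** No change to the plan is needed. The inconsistency between sections is real but editorial, and an analyst who follows Section 10.3 reaches one sound classification for every patient. A request to state which reading applies would add no better rule than the one already there.

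This rests on reading Section 10.3 as the governing scoring rule, which its express coverage of inpatients, its closing clause and the schedule footnote all support. The 1.5% to 4.3% range rests on an assumed weaning rate, on assumed inpatient shares up to the extreme of 100%, and on scoring the whole trial by the 5-minute check. It leaves out patients 24 hours off oxygen with saturation of 90% or lower, whose number the documents do not allow anyone to estimate. Under Section 10.3 those patients are successes in any case.

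### The primary analysis ignores the baseline oxygen category already scheduled for collection; a pre-specified stratified analysis, reported with the risk difference and its 95% CI, would be a cheap improvement

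*Combined protocol and SAP*

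**What the plan says.** Section 10.3 describes the primary analysis in two sentences: "The primary analysis will report the number and percentage of patients meeting the primary endpoint" and "The chi-square statistic will be used to test the difference between the two treatment groups". It adds a Kaplan-Meier display and a two-sided threshold of p < 0.049. It names no covariate, stratified analysis, effect measure or interval for this endpoint. The one sentence on intervals, "Therefore, these results will be displayed as point estimates with 95% confidence intervals", follows from a statement about the secondary and exploratory endpoints.

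The plan also says what the estimate is for. Section 10.3 states that "an important aspect of this study is to better define the magnitude of the treatment effect" and that the day-14 comparison is meant "to expeditiously inform whether a larger study should be undertaken". Section 10.1 asks for complete follow-up "given the importance of reliable estimates of the treatment effect for planning futures".

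On baseline oxygen, Section 5.1 admits patients with low room-air saturation or any need for supplemental oxygen, and Section 5.2 excludes those on mechanical ventilation. Patients can therefore enter in category 2 (no oxygen), 3 (oxygen) or 4 (high-flow or non-invasive ventilation) of the scale in Section 2. Table 7-1 schedules "Clinical assessment (6 category ordinal scale") at screening and Day 0. Section 10.2 gives a general rule: "Baseline value is defined as the last non-missing assessment prior to the first dose of study drug unless specified otherwise".

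**The concern.** The entry oxygen category is the baseline state of the quantity that the endpoint measures. A patient who enters on high-flow oxygen has further to go to be off oxygen by day 14 than one who enters on none. With 30 patients per arm, chance imbalance on such a variable can move the observed difference, and an unadjusted test does nothing about it. Randomisation is stratified by site only (Section 6.2.4).

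At stake is some power, chiefly if the true effect is smaller than 40 points, and a comparison that readers will want in any case. If the plan does not define that comparison, it may be chosen after the data are seen. Because the trial is meant to size later work, the scale and interval of the headline estimate should be fixed at the same time.

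**Working it through.** **Inputs from Section 10.3.** 40% versus 80%, 30 per arm, two-sided alpha 0.05 in the sample-size statement and 0.049 in the analysis, stated power at least 80%.

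**1. The plan's own figure.** With pooled variance, power = Φ[(0.40 − z·√(2·0.6·0.4/30)) / √((0.4·0.6 + 0.8·0.2)/30)].

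- At alpha 0.05: (0.40 − 1.960 × 0.1265)/0.1155 = 1.317, so power is 90.6%.
- At alpha 0.049: 90.4%.
- Exact enumeration of two Binomial(30) counts with the Pearson statistic at 0.049: 90.5% at 80% versus 40%, 66.3% at 70% versus 40%, and type I error 4.9% at 40% versus 40%.
- With the Yates correction or Fisher's test: 85.1% at 80% versus 40%.

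The stated power holds in every variant.

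**2. Headline estimate at the planned rates.** For 24/30 versus 12/30 the difference is 40 points. Wilson limits are 0.627 to 0.905 and 0.246 to 0.577. The Newcombe limits are:

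- lower: 0.40 − √[(0.800 − 0.627)² + (0.577 − 0.400)²] = 0.153
- upper: 0.40 + √[(0.905 − 0.800)² + (0.400 − 0.246)²] = 0.586

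Exact coverage is 95.1% at 80% versus 40% and 94.1% at 70% versus 40%.

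**3. Stratified test.** Across oxygen categories k, z = Σ(aₖ − n₁ₖmₖ/nₖ) / √Σ[n₁ₖn₀ₖmₖ(nₖ − mₖ)/(nₖ²(nₖ − 1))]. Here aₖ is treated successes, mₖ is all successes, and n₁ₖ, n₀ₖ and nₖ are the treated, placebo and total numbers.

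The documents give no entry mix and no prognostic strength, so both are assumed. Five mixes (categories 2/3/4, in %) were crossed with a fall of 0, 1 or 2 log-odds of success per oxygen step, which is an odds ratio of 1, 2.7 or 7.4 per step. Outcomes were logistic and calibrated to the marginal rates, with 20,000 simulated trials per scenario. Category 2 or 4 was merged into 3 if it held fewer than 5 patients or none in one arm. CMH power minus chi-square power, in points:

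| Mix 2/3/4 | 80% vs 40%: 0 / 1 / 2 log-odds | 70% vs 40%: 0 / 1 / 2 log-odds |
|---|---|---|
| 15/50/35 | -1.1 / +1.0 / +5.4 | -2.1 / +2.0 / +10.7 |
| 10/70/20 | -0.8 / +0.9 / +3.7 | -2.0 / +0.7 / +5.9 |
| 30/50/20 | -1.0 / +1.6 / +5.7 | -2.0 / +1.9 / +11.8 |
| 2/68/30 | -0.5 / +0.7 / +3.9 | -1.2 / +0.4 / +6.0 |
| 2/88/10 | -0.3 / +0.2 / +1.4 | -0.6 / -0.1 / +1.3 |

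At 0.5 log-odds per step the change is -0.4 to -0.1 points at 80% versus 40% and -1.6 to -0.6 at 70% versus 40%. With equal arms at 40%, CMH rejects in about 4.7-5.2% of trials.

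**4. How often merging applies.** A category holding 2% of 60 patients has fewer than 5 members with probability P(Binomial(60, 0.02) ≤ 4) = 0.993. The rule applies in about 5% of trials for 15/50/35, 29% for 10/70/20 and under 1% for 30/50/20.

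**The case against.** The strongest reply is that nothing here is broken. The chi-square is valid, and one test and one threshold are named. At the design effect power is already 90.5%, so there is little to gain. The benefit rests on inputs that the documents do not contain. At 0.5 log-odds per step or less the stratified test gains nothing, and gains above about 2.5 points need 1.5 to 2 log-odds per step. All of that stands, and it is why this is only a suggestion.

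The missing interval is also a small matter taken alone. The plan reports both counts, is designed around a difference in percentages, and lets any reader compute the crude interval. A reader might infer that the trial cannot deliver its effect size. The documents do not support that; one sentence closes the gap.

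A reader might also expect adjustment to tighten the estimate. It does not do so reliably. The mean half-width of the Mantel-Haenszel interval at 80% versus 40% is 22.3-22.6 points at 0 log-odds, 21.6-22.1 at 1 and 20.0-21.7 at 2, against 21.4 for crude Newcombe. Its coverage is 93.3-94.4%. The crude interval should therefore be the headline.

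Finally, choosing the smaller of the two p-values would raise type I error to 5.2-7.4%. This is not a defect of the current plan, which has a single test. It becomes a risk only once a second test is added, so the addition must say which test decides.

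**Conclusion.** The point holds as a low-cost improvement. Section 10.3 leaves unused a scheduled baseline value that is directly related to the endpoint. Under the assumed mixes and strengths, CMH changes power as follows:

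- 80% versus 40%: about -1 to 0 points if oxygen category is not prognostic, 0 to +2 at 1 log-odds per step, +1 to +6 at 2 log-odds per step.
- 70% versus 40%: about -2 to -1, 0 to +2, and +1 to +12.

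The gain nearly vanishes if almost all patients enter in one category. Type I error is not materially affected.

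A reader might infer that the chi-square is wrong or the trial underpowered; the exact power of 90.5% against a stated 80% rules that out. A reader might also take the day-14 result to settle whether a larger trial follows. Section 10.3 says only that it will inform that choice. The number of sites is not stated, so adding site as a stratum was not assessed.

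**What to change.** Before unblinding, add a short paragraph to Section 10.3:

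1. Report the crude risk difference with a Newcombe 95% CI as the headline estimate for the primary endpoint.
2. Pre-specify a CMH analysis stratified by baseline oxygen category alone (2/3/4), reported beside the chi-square. Define baseline here as the last value before randomisation, an exception that the wording of Section 10.2 permits.
3. State a rule for sparse or empty categories, for example: merge category 2 or 4 into 3 if it holds fewer than 5 patients in total or none in one arm.
4. State that the chi-square decides at p < 0.049, unless CMH is named as the deciding test before unblinding.

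The cost is a few lines of text and code, with no new data or patients. If the chi-square remains the deciding test, no power is lost. If CMH decides and oxygen category is not prognostic, the loss is up to about 1 point at 80% versus 40% and 2 points at 70% versus 40%. The example merging rule would almost always apply to a category holding about 2% of patients, leaving two strata or fewer.
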